4.1.1.1. Treatment Group A: Azacitidine

Dose escalation will begin with starting doses of azacitidine 75 mg SC or IV for 5 days (5 doses may be administered over the Day 1-7 period) of the first 2 cycles, pembrolizumab 200 mg IV Q3W, and epacadostat 100 mg orally (PO) BID continuous dose administration. If the starting dose proves intolerable, then azacitidine 50 mg SC or IV for 5 days, pembrolizumab 200 mg IV Q3W, and epacadostat 100 mg PO BID will be evaluated. The cohorts and dose levels are shown in Table 1.

Table 1: Dose Levels: Treatment Group A

Cohort	Azacitidine	Pembrolizumab	Epacadostat
-2-	50 mg SC or IV for 5 days (5 doses over Day 1-7 period) in Cycle 1 & 2	200mgIVQ3W	50 mgPOBID
-1"	50 mg SC or IV for 5 days (5 doses over Day 1-7 period) in Cycle 1 & 2	200mgIVQ3W	100mgPOBID
1	75 mg SC or IV for 5 days (5 doses over Day 1-7 period) in Cycle 1 & 2	200 mgIVQ3W	100 mg POBID
2Ab	75 mg SC or IV for 5 days (5 doses over Day 1-7 period) in Cycle 1 & 2	200mgIVQ3W	300mgPOBID
2Bb	100 mg SC or IV for 5 days (5 doses over Day 1-7 period) in Cycle 1 & 2	200mgIVQ3W	100mgPOBID
3	100 mg SC or IV for 5 days (5 doses over Day 1-7 period) in Cycle 1 & 2	200mgIVQ3W	300mgPOBID

- If Cohort 1 proves intolerable, Cohort -1 may be evaluated. If Cohort -1 is not tolerable, Cohort -2 may be evaluated with epacadostat 50 mg PO BID. If a de-escalation cohort is determined to be safe and tolerable, the dose of azacitidine or epacadostat may be re-escalated in separate, additional cohorts based on the review of available safety data.
- For Cohort 2, escalation of azacitidine to 100 mg or epacadostat to 300 mg BID will be dependent on the observation of Grade 3 or greater immune-related or non-immune-related toxicities in Cohort 1 (toxicities that were not considered DLTs). If Grade 3 or greater immune-related toxicities are observed in Cohort 1, azacitidine will be escalated first (Cohort 2B). If non-immune-related Grade 3 or greater toxicities are observed, epacadostat will be preferentially escalated (Cohort 2A). Dose-escalation Cohorts 2A and 2B may be opened in parallel if no Grade 3 AEs are observed in Cohort 1.

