In Treatment Group A, subjects will receive the DNA methyltransferase inhibitor azacitidine in combination with the programmed death receptor-1 (PD-1) inhibitor pembrolizumab and the indoleamine 2,3-dioxygenase (IDO) 1 inhibitor epacadostat. Part 1 of Treatment Group A will consist of a dose-escalation assessment of the safety and tolerability of the treatments in subjects with advanced or metastatic solid tumors. In Part 1 of Treatment Group A, pembrolizumab and epacadostat will be administered in 21-day cycles from Cycle 1 Day 1 in combination with azacitidine. Subjects in Treatment Group A will receive up to 6 cycles of azacitidine as long as the subject is receiving benefit from treatment and has not met any criteria for study withdrawal (except for Expansion Cohorts A-4 and A-5, which will receive up to 5 cycles). In Part 2 of Treatment Group A will consist of Simon 2-Stage cohorts in previously treated NSCLC and MSS CRC. Separate treatment sequencing tumor biopsy cohorts are also included in Prut 2 to further evaluate epigenetic changes and changes in the tumor microenvironment in subjects with select solid tumors. In Treatment Group A, subjects who have an initial response or stable disease (SD) for greater than 6 months but later relapse while receiving pembrolizumab and epacadostat will have the opportunity to repeat the azacitidine epigenetic priming regimen to which they were originally assigned with medical monitor approval. Study treatment may continue as long as the subject is receiving benefit and has not met any criteria for study withdrawal or until the subject has received 35 administrations of pembrolizumab (approximately 2 years), whichever occurs first.

Treatment Groups B and C (Upon implementation of Amendment 4, these treatment groups are no longer applicable)

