During the study, dose interruptions and/or dose modifications may be implemented based on toxicity as described in the Protocol. However, dose modifications should not be made during the DLT observation period without discussion with the medical monitor. Intrasubject dose escalation is not permitted.

Treatment Group A: Azacitidine

In Treatment Group A, dose escalation will begin with starting doses of azacitidine 75 mg subcutaneous (SC) or intravenous (IV) injection for 5 days (5 doses may be administered over the Day 1-7 period) of the first 2 cycles, pembrolizumab 200 mg IV every 3 weeks (Q3W), and epacadostat 100 mg orally (PO) twice daily (BID) continuous dose administration. If the starting dose proves intolerable, azacitidine 50 mg SC or IV for 5 days, pembrolizumab 200 mg IV Q3W, and epacadostat 100 mg PO BID will be evaluated. The cohorts and dose levels are shown in the following table.

Treatment Group A: Azacitidine

Cohort	Azacitidine	Pembrolizumab	Epacadostat
-2	50 mg SC or IV for 5 days (5 doses over Day 1-7 period) in Cycle 1 & 2	200mg IV Q3W	50mg PO BID
-1	50 mg SC or IV for 5 days (5 doses over Day 1-7 period) in Cycle 1 & 2	200mg IV Q3W	100 mg PO BID
1	75 mg SC or IV for 5 days (5 doses over Day 1-7 period) in Cycle 1 & 2	200 mg IV Q3W	100 mg PO BID
	75 mg SC or IV for 5 days (5 doses over Day 1-7 period) in Cycle 1 & 2	200mg IV Q3W	300mg PO BID
	100 mg SC or IV for 5 days (5 doses over Day 1-7 period) in Cycle 1 & 2	200mg IV Q3W	100 mg PO BID
3	100 mg SC or IV for 5 days (5 doses over Day 1-7 period) Days 1-5 in Cycle 1 & 2	200mg IV Q3W	300mg PO BID

- If Cohort 1 proves intolerable, Cohort -1 may be evaluated. If Cohort -1 is not tolerable, Cohort -2 may be evaluated with epacadostat 50 mg PO BID. If a de-escalation cohort is determined to be safe and tolerable, the dose of azacitidine or epacadostat may be re-escalated in separate, additional cohorts based on the review of available safety data.

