INCB059872 (United States sites only) will be orally self-administered either QD or QoD beginning on Cycle 1 Day 1 and continuously thereafter in 21-day cycles. All daily doses will be taken in the morning at the same time as the morning dose of epacadostat, approximately 24 hours prior and 1 hour following dose administration, except on days when serial sampling is conducted, then subjects will fast at least 8 hours before and 1 hour after study drug or as indicated in the Protocol. If a dose is missed by more than 8 hours, then that dose should be skipped, and the next scheduled dose should be taken at the usual time. Details for study drug administration in the treatment sequencing tumor biopsy cohorts (Cohorts C-11 through C-13) are presented in the Overall Study Design section of the Synopsis and in the Protocol.

Reference Therapies, Dosage, and Mode of Administration:

Pembrolizumab will be administered as a 200 mg, 30-minute IV infusion Q3W on Day 1 of each 21-day cycle. Details for study drug administration in the treatment sequencing tumor biopsy cohorts (Cohorts A-3 through A-5, B-9 through B-11, and C-11 through C-13) are presented in the Overall Study Design section in the Synopsis and in the Protocol.

Azacitidine will be administered as a SC injection or IV infusion for 5 days in Cycles 1 through 3 (in the European Union, it will be administered SC only). Details for study drug administration in the treatment sequencing tumor biopsy cohorts (Cohorts A-3 through A-5) are presented in the Overall Study Design section of the Synopsis and in the Protocol. Subjects who remain on treatment beyond the Week 9 scan should continue to receive azacitidine until the second on-study scan (up to the Week 18 scan, for a maximum of 3 additional cycles). Five doses should be administered over the Day 1-7 period.

Re-treatment with azacitidine (based on original treatment assignment) along with pembrolizumab and epacadostat may be administered for subjects who had a CR, PR, or SD (for > 6 months) and later had evidence of progressive disease while receiving pembrolizumab and epacadostat with medical monitor approval. Three additional cycles of azacitidine are permitted.

Study Schedule/Procedures:

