The dose combination of epacadostat 100 mg BID plus pembrolizumab 200 mg Q3W for the Phase 3 melanoma study (INCB 24360-301) was chosen based on a benefit/risk assessment made specifically in melanoma in collaboration with Merck. In INCB 24360-202, there was evidence of improved efficacy in melanoma subjects at all doses of epacadostat from 50 to 300 mg BID. Given that melanoma is an immunotherapy-responsive tumor, and lower doses of epacadostat appeared to have similar activity, the decision was made to take the 100 mg BID dose combination forward because of the lower incidence of dose interruptions and dose reductions compared to the 300 mg BID dose.

However, in other tumor types that appear to demonstrate more resistance to known immunotherapies, greater target coverage for inhibition of IDO1 may be necessary. Pharmacokinetic/pharmacodynamic modelling suggests that doses of epacadostat 100 mg BID achieve an average IC₅₀ at trough in most patients. At 300 mg BID, epacadostat achieves target inhibition above the IC₉₀ at trough. Incyte believes that greater target inhibition may be necessary in more resistant tumors, and potentially balances benefit/risk in favor of the higher epacadostat dose combination given that the dose does not exceed the MTD.

The azacitidine starting dose of 75 mg per day on Days 1 to 5 for 2 cycles was selected based off of previous studies evaluating the combination of azacitidine and entinostat as a stand-alone regimen or as a priming regimen before the receipt of nivolumab. In a Phase 1/2 study evaluating azacitidine and entinostat in subjects with recurrent metastatic NSCLC, the combination of 40 mg/m² azacitidine administered on Days 1 to 6 and 8 to 10 and 7 mg of entinostat administered on Days 3 and 10 of each cycle was generally well-tolerated and no DLTs were observed (Juergens et al 2011). This dose regimen was chosen as RP2D, and a randomized Phase 2 study in subjects with recurrent metastatic NSCLC was initiated evaluating

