5.2.3. Azacitidine

5.2.3.1. Description and Administration

Azacitidine is provided as a lyophilized powder in 100 mg single-use vials to be administered by SC injection or IV infusion. In the European Union, azacitidine will be administered SC only.

Five doses of azacitidine will be administered in the clinic during Cycles 1 through 3. Details for study drug administration in the treatment sequencing tumor biopsy cohorts (Cohorts A-3 through A-5) are presented in Table 5 and the study assessments tables (see Section 6). Subjects who remain on treatment beyond the Week 9 scan should continue to receive azacitidine until the second on-study scan (up to the Week 18 scan, for a maximum of 3 additional cycles) and then continue pembrolizumab and epacadostat as long as there is benefit. The 5 doses should be administered over the Day 1 to 7 period. Re-treatment with azacitidine (based on original

treatment assignment) along with pembrolizumab and epacadostat may be administered for subjects who had a CR, PR, or SD (for > 6 months) and later had evidence of PD while receiving pembrolizumab and epacadostat with medical monitor approval. Three additional cycles of azacitidine are pennitted.

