3.1.2.1. Treatment Group A: Azacitidine

Dose escalation will begin with starting doses of azacitidine 75 mg SC or IV for 5 days (5 doses may be administered over the Day 1-7 period) of the first 2 cycles, pembrolizumab 200 mg IV Q3W, and epacadostat 100 mg PO BID continuous dose administration. If the starting dose proves intolerable, then azacitidine 50 mg SC or IV for 5 days, pembrolizumab 200 mg IV Q3W, and epacadostat 100 mg PO BID will be evaluated. The cohorts and dose levels are shown in [Table 1](#).

Table 1: Dose Levels: Treatment Group A

Cohort	Azacitidine	Pembrolizumab	Epacadostat
-2 ^a	50 mg SC or IV for 5 days (5 doses over Day 1-7 period) in Cycle 1 & 2	200 mg IV Q3W	50 mg PO BID
-1 ^a	50 mg SC or IV for 5 days (5 doses over Day 1-7 period) in Cycle 1 & 2	200 mg IV Q3W	100 mg PO BID
1	75 mg SC or IV for 5 days (5 doses over Day 1-7 period) in Cycle 1 & 2	200 mg IV Q3W	100 mg PO BID
2A ^b	75 mg SC or IV for 5 days (5 doses over Day 1-7 period) in Cycle 1 & 2	200 mg IV Q3W	300 mg PO BID
2B ^b	100 mg SC or IV for 5 days (5 doses over Day 1-7 period) in Cycle 1 & 2	200 mg IV Q3W	100 mg PO BID
3	100 mg SC or IV for 5 days (5 doses over Day 1-7 period) in Cycle 1 & 2	200 mg IV Q3W	300 mg PO BID

^a If Cohort 1 proves intolerable, Cohort -1 may be evaluated. If Cohort -1 is not tolerable, Cohort -2 may be evaluated with epacadostat 50 mg PO BID. If a de-escalation cohort is determined to be safe and tolerable, the dose of azacitidine or epacadostat may be re-escalated in separate, additional cohorts based on the review of available safety data.

^b For Cohort 2, escalation of azacitidine to 100 mg or epacadostat to 300 mg BID will be dependent on the observation of Grade 3 or greater immune-related or non-immune-related toxicities in Cohort 1 (toxicities that were not considered DLTs). If Grade 3 or greater immune-related toxicities are observed in Cohort 1, azacitidine will be escalated first (Cohort 2B). If nonimmune-related Grade 3 or greater toxicities are observed, epacadostat will be preferentially escalated (Cohort 2A). Dose-escalation Cohorts 2A and 2B may be opened in parallel if no Grade 3 AEs are observed in Cohort 1.

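### For Part 1 and Cohorts A-1 and A-2, the dose-level text and tables give azacitidine for two cycles, but the administration section gives three, plus up to three more

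*Protocol*

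**What the plan says.** **Two cycles.** Protocol 4.1.1.1 describes the starting regimen with "5 doses may be administered over the Day 1-7 period) of the first 2 cycles", and each of the six dose levels in Table 1 names Cycles 1 and 2. The synopsis section on azacitidine dose escalation has the same sentence, "for 5 days (5 doses may be administered over the Day 1-7 period) of the first 2 cycles", and a matching table. SAP 3.1.2.1 repeats it, "may be administered over the Day 1-7 period) of the first 2 cycles", with its own six-row Table 1.

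**Three cycles, then up to three more.** Protocol 5.2.3.1, which governs azacitidine administration, says "Five doses of azacitidine will be administered in the clinic during Cycles 1 through 3". It extends treatment for subjects who stay on study drug after the Week 9 scan: "up to the Week 18 scan, for a maximum of 3 additional cycles". The synopsis section on reference therapies gives the same base course, "Azacitidine will be administered as a SC injection or IV infusion for 5 days in Cycles 1 through 3", and the same extension. These are the only two places that state the rule in full.

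**Partial support.** The azacitidine note in Table 29, a schedule titled for Part 1, A-1 and A-2, gives Cycles 1 to 3 and does not mention the extension. The synopsis, Protocol 4.1 and SAP 3.1.1.1 state only the ceiling: "Subjects in Treatment Group A will receive up to 6 cycles of azacitidine", with 5 for A-4 and A-5.

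**The concern.** The number of cycles is an instruction to sites, and two current sections answer it differently. Each dose-level row states a schedule as well as a milligram dose, so anyone working from Table 1 would stop azacitidine after Cycle 2 and omit at least the Cycle 3 doses.

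Some visit text points the same way. Azacitidine is given in the clinic, yet the synopsis visit list for Part 1 provides the extra early-cycle visits only in Cycles 1 and 2 and a Day 1 visit in every later cycle. Protocol 6.2 likewise limits additional visits to Cycles 1 and 2. Elsewhere, the synopsis paragraph on study visits runs to Cycle 3, or to Cycle 6 for subjects who continue azacitidine.

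The SAP also disagrees with itself: 3.1.1.1 allows up to 6 cycles, while 3.1.2.1 and Table 1 give 2. SAP 5.2 uses that Table 1 to name the reporting groups.

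**Working it through.** **Inputs**
- Doses per cycle: 5 (Protocol 4.1.1.1, Table 1 and 5.2.3.1). The five doses in 5.2.3.1 are read as per cycle, because they are tied to Days 1 to 7.
- Dose-level text: 2 cycles (Protocol 4.1.1.1 and Table 1; synopsis; SAP 3.1.2.1 and Table 1).
- Base course: 3 cycles (Protocol 5.2.3.1; synopsis; Table 29 note).
- Extension: at most 3 cycles (Protocol 5.2.3.1; synopsis).
- Stated ceilings: 6 cycles, or 5 in A-4 and A-5 (Protocol 4.1).

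**Step 1. Reproduce the plan's own ceiling.**
- Part 1, A-1, A-2: 3 + 3 = 6.
- A-3 (Week -1, then Cycles 2 and 3, then the extension): 1 + 2 + 3 = 6.
- A-4 and A-5 (Cycles 2 and 3, then the extension): 2 + 3 = 5.

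All three match the stated ceilings. A two-cycle schedule cannot produce 6.

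**Step 2. Planned doses in initial treatment, Part 1, A-1 and A-2** (doses = cycles × 5; total = doses × mg)

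| Source | Cycles | Doses | Total at 75 mg | Total at 100 mg |
|---|---|---|---|---|
| Dose-level text and tables | 2 | 10 | 750 mg | 1,000 mg |
| 5.2.3.1, base course | 3 | 15 | 1,125 mg | 1,500 mg |
| 5.2.3.1, full extension | 6 | 30 | 2,250 mg | 3,000 mg |

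**Step 3. Gap.**
- Scheduled: 15 − 10 = 5 doses; 5/15 = 33%.
- Conditional maximum: 30 − 10 = 20 doses; 20/30 = 67%. This applies only to a subject who stays on treatment beyond the Week 9 scan and receives all three extra cycles.

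**Step 4. How often the two-cycle wording occurs.** Six rows in each of three tables gives 18 cells. One sentence each in the synopsis, Protocol 4.1.1.1 and SAP 3.1.2.1 adds 3. Total: 18 + 3 = 21.

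**Step 5. What depends on the count.**
- The Group A DLT window is Cycle 1, through Day 21 (Protocol 5.4.1.1). Its azacitidine requirement is 4 of the 5 Cycle 1 doses. Neither changes.
- No sample size, Type I error or power figure uses azacitidine cycles.
- SAP 6.4.3 summarizes azacitidine doses actually given, and SAP 6.5 does not calculate azacitidine compliance.

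**The case against.** **Table 1 only defines dose levels, so its schedule has no force.** This stands in part. It is a dose-level table under dose escalation. A-1 and A-2 take their dose through Table 4, and both the administration section and the schedule that covers Part 1 give three cycles. A careful site would probably follow those. But every row of Table 1 states the cycles, so it is not silent on schedule.

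**Two cycles might be a Part 1 rule or the DLT period.** Neither reading works. Table 29 names Part 1 and gives Cycles 1 to 3, and the DLT window is one cycle.

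**This only compares an amendment log with current text.** It does not. The Amendment 2 entry in Appendix E, which raises the maximum from 2 to 6, explains where the wording probably came from. The conflict is between live sections and stands without that entry.

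**Protocol 1.7.2 should not be counted as an error.** This stands. A reader might add "The azacitidine starting dose of 75 mg per day on Days 1 to 5 for 2 cycles was selected" to the list. That sentence explains in the past tense why the starting dose was chosen, and the same section describes a precedent trial that used two priming cycles. Rewriting it to the present schedule would credit that precedent with a regimen it did not use.

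**The SAP wording has no analytic effect.** This also stands. SAP 3.5 refers to the protocol for schedules, and SAP 5.2 uses Table 1 only to identify dose levels.

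**Conclusion.** The two-cycle wording in Protocol 4.1.1.1 and Table 1, the synopsis dose-escalation text and table, and SAP 3.1.2.1 and Table 1 is wrong as written for Part 1, A-1 and A-2. The scheduled shortfall is 5 of 15 doses (33%); 20 of 30 (67%) is a conditional maximum. The figures assume five doses in every planned cycle and initial treatment only, leaving out the three re-treatment cycles that 5.2.3.1 also permits. Cohorts A-3, A-4 and A-5 follow their own sequences in Protocol Table 5, so the Cycles 1 to 3 rule should not be applied to them.

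The point is minor. Two stronger readings are tempting, and the documents support neither:
- **That subjects were under-dosed.** Neither document reports how many cycles any subject received or which section any site followed.
- **That the MTD or the results are compromised.** The MTD rule rests on Cycle 1 toxicity. Protocol 5.4.1.1 allows a lower MTD from toxicity seen after Day 21, but that provision depends on events observed, not on a planned cycle count. No SAP calculation takes the planned count as an input.

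Enrollment had also stopped and the study was ended early (SAP 4.1 and 5.2), which limits the practical benefit of correcting the text now.

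**What to change.** - **Protocol 4.1.1.1, Table 1 and the matching synopsis text and table:** replace the two-cycle wording with the 5.2.3.1 schedule. Alternatively, remove the cycle count and refer to 5.2.3.1 and, for the sequencing cohorts, Table 5.
- **SAP 3.1.2.1 and Table 1:** define dose levels by milligram dose only and refer to the protocol for the schedule. This also removes the conflict with SAP 3.1.1.1.
- **Table 29 azacitidine note:** add the extension of up to three cycles, as the corresponding notes for A-3, A-4 and A-5 already do.
- **Protocol 6.2 visit sentence and the synopsis Part 1 visit list:** align both with the synopsis statement that extra visits run to Cycle 3, or to Cycle 6 for those who continue azacitidine after the first scan.
- **Protocol 1.7.2:** leave the rationale as it is, or at most add a sentence noting the later extension.

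The cost is wording changes in two documents. No new data, analysis, subgroup or output is needed, because actual azacitidine exposure is already summarized under SAP 6.4.3.

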4.1.1.2. Treatment Group B: INCB057643

In Treatment Group B, dose escalation will begin with a starting dose of INCB057643 of 4 mg PO QD continuous dose administration beginning on Cycle 1 Day 1 for the first 21-day cycle. Beginning on Cycle 2 Day 1, pembrolizumab 200 mg IV Q3W and epacadostat 100 mg PO BID continuous dose administration will be added to INCB057643. If the starting dose level proves intolerable, INCB057643 4 mg PO QD in combination with pembrolizumab 200 mg IV Q3W and epacadostat 50 mg PO BID will be evaluated. The cohorts and dose levels are shown in Table 2.

Table 2: Dose Levels: Treatment Group B

Cohort	INCB057643	Pembrolizumab	Epacadostat
-I"	4mgPOQD beginning C3D1	200mgiVQ3W beginning C2D1	50 mgPO BID beginning C2D1
1	4 mg PO QD beginning C1D1	200mgiVQ3W beginning C2D1	100 mgPOBID beginning C2D1
2	8mgPOQD beginning C1D1	200mgiVQ3W beginning C2D1	100mgPOBID beginning C2D1
3	12mgPO QD beginning C1D1	200mgiVQ3W beginning C2D1	100mgPOBID beginning C2D1

a If Cohort I proves intolerable, Cohort -I may be evaluated. If Cohort -I is not tolerable, lower doses or alternative dose schedules of INCB057643 may be tested; however, at this time, 4 mg tablets are the lowest dose formulation available. Any dose reduction in INCB057643 would be combined with pembrolizumab 200 mg IV Q3W and epacadostat 50 mg PO BID. If a de-escalation cohort is determined to be safe and tolerable, the dose of INCB057643 or epacadostat may be re-escalated in separate, additional cohorts based on the review of available safety data.

4.1.1.3. Treatment Group C: INCB059872

In Treatment Group C, dose escalation will begin with a starting dose of INCB059872 of 1 mg PO QoD continuous dose administration beginning on Cycle 1 Day 1 for the first 21-day cycle. Beginning on Cycle 2 Day 1, pembrolizumab 200 mg IV Q3W and epacadostat 100 mg PO BID continuous dose administration will be added to INCB059872. If the starting dose level proves intolerable, INCB059872 1 mg PO QoD in combination with pembrolizumab 200 mg IV Q3W and epacadostat 50 mg PO BID will be evaluated. The cohorts and dose levels are shown in [Table 3](#).

Table 3: Dose Levels: Treatment Group C

Cohort	INCB059872	Pembrolizumab	Epacadostat
-I"	1 mgPO QoD beginning C1D1	200mgiVQ3W beginning C2D1	50 mgPO BID beginning C2D1
1	1 mgPOQoD beginning C1D1	200mgiVQ3W beginning C2D1	100 mgPOBID beginning C2D1
2Ab	2 mgPO QoD beginning C1D1	200mgiVQ3W beginning C2D1	100mgPO BID beginning C2D1
2Bb	1 mgPO QD beginning C1D1	200mgiVQ3W beginning C2D1	100mgPOBID beginning C2D1
3c	3 mgPO QoD beginning C1D1	200mgiVQ3W beginning C2D1	100mgPO BID beginning C2D1

a If Cohort I proves intolerable, Cohort -I may be evaluated. If Cohort -I is not tolerable, lower doses or alternative dose schedules of INCB059872 may be tested. Any dose reduction in INCB059872 would be combined with pembrolizumab 200 mg IV Q3W and epacadostat 50 mg PO BID. If a de-escalation cohort is determined to be safe and tolerable, the dose of INCB059872 or epacadostat may be re-escalated in separate, additional cohorts based on the review of available safety data.

b Dose-escalation Cohorts 2A and 2B may be opened in parallel if no Grade 3 AEs are observed in Cohort I.

c Cohort 3 will be enrolled once Cohort 2A clears the DLT period. Enrollment into Cohort 3 is not dependent upon clearing the DLT period from Cohort 2B.

